**10. How long ago was your most recent injury?**

\_\_\_\_\_ /months

**11. Mechanism of injury**

loss of control       loss of traction       collision with object       collision with rider       mechanical problem  
 unknown       other \_\_\_\_\_

**12. Severity of injury** (if more than one injury occurred, choose the most severe one)

no medical treatment needed     self-administered medical treatment     MD administrated medical treatment     Medical treatment in ER     Overnight hospitalization

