## **1. Introduction**

Mountain biking has developed into a popular sport performed by both amateurs and professionals. Physical activity is often related to an increasing risk of injury which may lead to high socioeconomic costs. To avoid accident-related injuries, each racing discipline demands its own set of specific skills and training regimens. The aim of this study is to perform a descriptive analysis of the causes and effects of mountain biking related injuries in amateur and professional athletes.

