## **2. Methods**

A survey (as outlined below) of mountain biking related injuries will be conducted on the participants of the Swiss Epic mountain bike event in 2017 held in Valais. The retrospective questionnaire is designed in accordance with existing literature ((Gaulrapp et al., 2001; Lareau and McGinnis, 2011), will include 25 questions and will be translated into English, French, Italian, Spanish and German. The participants will be asked to tick the most appropriate answer. The questionnaire aims to assess the athletes' 1) basic demographics, riding level and years of experience, 2) number of races per year and mean hours of training per week, 3) number and kind of suffered injuries related to mountain biking and medical treatment requirement, 4) and amount and kind of protective gear items.

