**9. Number of injuries obtained during mountain biking**

\_\_\_\_\_

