**13. Body location affected**

hand/finger     calf and knee     hip and thigh     trunk     foot and ankle joints  
 shoulder     head     internal organs     upper arm and forearm

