**14. Type of injury**

bone fractures     joint injuries     skin and soft tissue injuries     concussion

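### The questionnaire does not say which injury items 11 and 13–17 describe when a rider has had several, so its injury tables can mix latest and worst injuries

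*Combined protocol and SAP*

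**What the plan says.** The Introduction sets the aim: to "perform a descriptive analysis of the causes and effects of mountain biking related injuries". The Methods list, among the things to be assessed, "number and kind of suffered injuries related to mountain biking and medical treatment requirement".

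On the questionnaire the injury block runs as follows.

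| Item | Content | Injury named |
|---|---|---|
| 9 | "Number of injuries obtained during mountain biking" | all; open count, no recall period |
| 10 | "How long ago was your most recent injury" | the latest |
| 11 | "Mechanism of injury" | none |
| 12 | Severity, five grades | the worst: "if more than one injury occurred, choose the most severe one" |
| 13 | "Body location affected" | none |
| 14 | "Type of injury" | none |
| 15, 16 | Days until return to sport and to work | none |
| 17 | Recovery | refers to the injury without saying which |

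The form's opening instruction asks for a single best answer per item and sets no index injury. Neither the Methods nor section 3 (Statistical analysis plan) defines one or says how answers from riders with several injuries are handled. Section 3 plans descriptive statistics, correlations between the outcome variables, t-tests of injury-related variables between elite and amateur riders, and logistic regressions with severe injury as the dependent variable.

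**The concern.** A rider whose latest injury was a graze and whose worst was a fracture can properly answer item 10 for the first and item 12 for the second. For the other items the rider must choose, and nothing on the form records the choice. The analyst cannot undo it later.

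The main harm is to the descriptive aim. Mechanism is the form's item on the cause of injury; type, location, days lost and recovery carry the effects. A table of worst injuries and a table of latest injuries are different summaries, and a blend of the two in unknown proportion is neither.

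Two further harms are conditional. If elite and amateur riders differ in injury counts, the scope for mixing differs too, so a group contrast in days lost could partly reflect which injury was described. And if items 11 or 13–17 enter a correlation or regression with item 12 severity, predictor and outcome may belong to different injuries, which dilutes the association. Section 3 permits such predictors but names none.

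**Working it through.** The gap itself follows from the item wording and needs no arithmetic. The documents give no injury counts and no figure to reproduce, so the size below rests on assumed inputs.

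**Assumptions.** Injuries per injured rider are K = 1 + Poisson(λ), with λ = 1, 2, 4 (means 2, 3, 5). Injury order is unrelated to severity. A latent logistic severity is cut at −0.8, 0.6, 2.2 and 3.5 into five grades, as in item 12. Severe means the top two grades. Ties for worst are broken at random. Each scenario simulates 1,000,000 injured riders.

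**Step 1: how often the two readings point to different injuries.** Each of K injuries is equally likely to be the worst, so

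P(latest is not worst) = 1 − E(1/K) = 1 − (1 − e^(−λ))/λ

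- λ = 1: 1 − 0.632/1 = 0.368
- λ = 2: 1 − 0.865/2 = 0.568
- λ = 4: 1 − 0.982/4 = 0.755

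Simulation gives 0.369, 0.568 and 0.755. These figures count same-grade ties as different injuries. The recorded grade of the latest and worst injury differs in 29%, 46% and 64%.

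**Step 2: effect on a frequency table.** If a random fraction q of riders describe the latest injury and the rest the worst,

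tabulated % = (1 − q) × (% among worst) + q × (% among latest)

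The percentage among latest injuries equals that among all injuries.

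| Feature | q | Mean 2 | Mean 3 | Mean 5 |
|---|---|---|---|---|
| 40% of injuries, odds ratio 3 | 0 | 46.3% | 50.5% | 55.5% |
| | 25% | 44.8% | 47.9% | 51.5% |
| | 100% | 40% | 40% | 40% |
| 40% of injuries, odds ratio 1.5 | 0 | 42.4% | 44.0% | 45.8% |
| | 25% | 41.8% | 43.0% | 44.3% |
| 10% of injuries, odds ratio 10 | 0 | 14.9% | 18.8% | 24.5% |
| | 25% | 13.7% | 16.6% | 20.8% |
| | 50% | 12.4% | 14.4% | 17.2% |
| | 100% | 10% | 10% | 10% |

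For the 10% feature with odds ratio 5, the q = 0 figures are 13.6%, 16.2% and 19.9%. With odds ratio 1 there is no shift.

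**Step 3: effect on a severity model, if these items are used.** The feature is present in 40% of injuries, the per-injury odds ratio is 3, and the outcome is the worst injury's severity.

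| q | Mean 2 | Mean 3 | Mean 5 |
|---|---|---|---|
| 0 | 2.53 | 2.26 | 1.98 |
| 25% | 2.34 | 2.04 | 1.80 |
| 50% | 2.16 | 1.87 | 1.64 |
| 100% | 1.86 | 1.57 | 1.38 |

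Mispairing costs about 0.2 at q = 25% (2.53 − 2.34 = 0.19; 2.26 − 2.04 = 0.22; 1.98 − 1.80 = 0.18) and 0.6 to 0.7 at q = 100%. The rest of the fall from 3 comes from selecting the worst injury and would remain with perfect alignment.

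**Step 4: what is clean without a fix.** P(K = 1) = e^(−λ) = 0.368, 0.135, 0.018. With 16% of injuries severe (the step 3 setting), that leaves about 5.9, 2.2 and 0.3 severe events per 100 injured riders.

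**The case against.** The strongest reply is that item 12's rule carries forward. Items 13–17 follow it directly, and item 17 presupposes an injury already identified. This is a natural reading and lessens the exposure of those items. But the form does not state it, and it cannot cover item 11, which comes before the rule and straight after the question about the latest injury.

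A second reply is that item 12 may mean several injuries in the same, most recent accident, which would make items 10–17 one coherent block. The wording allows this. It adds a possible reading, so it strengthens the case for naming the index injury. If it is what the authors meant, the stem proposed below would change what is measured, so they should confirm their intention first.

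On size, three points stand. The shift depends on the feature being related to severity: for a 40% mechanism with odds ratio 1.5 and a quarter of riders describing the latest injury, it is only 0.6 to 1.5 points. The largest shifts use an odds ratio of 10, which suits type or location better than mechanism. And no calculation covers the days-lost items or estimates how many riders would actually answer for the latest injury. The regression harm is conditional, and rider-level predictors (demographics, experience, training, races, gear) are untouched.

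**Conclusion.** The concern holds and should be fixed. That the form names no injury for items 11 and 13–17 is certain from the text. Item 11 is clearly exposed; items 13–17 are exposed to a lesser degree. Riders with one injury, or whose latest injury is also their worst, are not affected.

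The size is uncertain. It rests on assumed injury counts, injury order unrelated to severity, and assumed links between features and severity. Across the cases shown, the gap between describing all worst and all latest injuries runs from about 2 points (42.4% against 40%) to about 15 points (55.5% against 40%, or 24.5% against 10%). It is zero for a feature unrelated to severity. These figures bound what could happen and do not predict it. The lasting problem is that the data would not show where in that range a table lies.

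**What to change.** Leave item 10 as it is and put one stem between items 10 and 11: *If you have never been injured, go to question 18. If you have had more than one injury, answer questions 11–17 for your MOST SEVERE injury.* This extends the rule printed in item 12, fits the severe-injury outcome in section 3, and settles the same-accident reading. Sending uninjured riders to item 18 is harmless because that item offers a negative answer.

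In the statistical analysis plan, define items 11–17 as features of the worst injury among injured riders, label the tables accordingly, and do not treat item 10 as the date of that injury unless item 9 equals 1.

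The cost is one stem in five languages; no item is deleted or reworded. The tables will describe worst rather than typical injuries, and the stem does not restore the per-injury odds ratio: with full alignment an odds ratio of 3 still appears as about 2.5, 2.3 or 2.0.

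If data are already collected, state the limitation and report the descriptive tables separately for riders with item 9 equal to 1, giving their number. Under the assumptions above that subset is 37%, 14% or 2% of injured riders, too few for regressions in elites and amateurs separately.

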## **3. Statistical analysis plan**

Data analyses will be performed using the Statistical Package for Social Sciences (SPSS), version 24.0 (IBM Corporation, Armonk, NY, USA).

Descriptive statistics [means  $\pm$  standard deviations (SD) and relative frequencies (%)] will be retrieved. Pearson correlations will be used to assess correlations between the outcome variables. Chi-squared tests will be applied to determine group differences of injury prevalence and the occurrence of severe, respectively mild injury events. Multivariate logistic regressions will be performed to evaluate predictive factors among the outcome variables (independent variables) of severe injury events (dependent variable; no severe injury = 0 versus severe injury = 1) in elites and amateurs separately. Independent samples t-tests will be used to evaluate mean group differences in demographics, and training and injury related variables between the elite and the amateur mountain bikers. P-values  $< 0.05$  will be considered as statistically significant. According to Cohen (1992), effect sizes will be calculated for the correlation analyses and defined as follows;  $r = 0.20$  small,  $r = 0.50$  medium,  $r = 0.80$  strong.

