**15. Days return to sports**

\_\_\_\_\_ days

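### The form's only severity item grades level of medical care, so a difference in access to care could be reported as a difference in injury severity

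*Combined protocol and SAP*

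**What the plan says.** Item 12 asks the rider to grade one injury: "if more than one injury occurred, choose the most severe one". The answers are "no medical treatment needed", "self-administered medical treatment", "MD administrated medical treatment", "Medical treatment in ER" and, at the top, a night in hospital. Section 2 (Methods) describes this part of the form as covering "number and kind of suffered injuries related to mountain biking and medical treatment requirement".

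Section 3 (Statistical analysis plan) speaks of severe and mild injuries. It plans chi-squared tests of group differences in them, without naming the groups in that sentence. It also plans logistic regressions to "evaluate predictive factors among the outcome variables (independent variables) of severe injury events", with severe injury coded 0 or 1, fitted in elites and amateurs separately. It does not name item 12 as the source or say which answers count as severe.

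The form also collects injury type (item 14), "15. Days return to sports", days to return to work (item 16) and recovery (item 17). Section 3 gives none of these a role in defining or checking severity. No item asks about access to care, such as medical cover at races, a team doctor or insurance.

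**The concern.** The care a rider receives depends on the injury, but also on who is available and on whether the rider seeks help. A moderate injury shown to a doctor scores level 3; the same injury treated by the rider scores level 2. If elites and amateurs differ in access or care-seeking, the chi-squared comparison could show a difference in severe injury where the injuries are alike. Within each group, a predictor such as races per year (item 7) could be associated with severe injury because riders who race more are closer to medical care. With access unrecorded, neither analysis can be adjusted.

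The form's introduction says the results may help improve safety and prevent injury. A factor that only tracks access to a doctor would mislead such advice.

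**Working it through.** The documents give no sample size, event rate or expected difference, so there is no planned figure to reproduce. Every rate and group size below is an assumption. Counts are injured riders, true severity is identical in both groups, and tests are two-sided at 0.05.

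**Illustration A: severe = doctor-treated or above, 150 per group.** Assume 20% of injuries are serious and always seen by a doctor, 40% are moderate and seen at a rate that depends on access, and 40% are minor and never seen. The rate of severe injury is 0.20 + 0.40 × (share of moderate injuries seen). Amateurs are held at 50% seen: 0.20 + 0.40 × 0.50 = 0.40.

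- Elites 80% (30-point gap): 0.20 + 0.40 × 0.80 = 0.52. Odds ratio (0.52/0.48)/(0.40/0.60) = 1.63. Pooled rate 0.46; SE = √(0.46 × 0.54 × 2/150) = 0.0575; z = 0.12/0.0575 = 2.09; P about 0.04.
- Elites 70% (20-point gap): 0.20 + 0.40 × 0.70 = 0.48. Odds ratio (0.48/0.52)/(0.40/0.60) = 1.38. Pooled rate 0.44; SE = √(0.44 × 0.56 × 2/150) = 0.0573; z = 0.08/0.0573 = 1.40; P about 0.16.

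**Illustration B: 100 elites and 300 amateurs.** Assume 15% reach an emergency room or hospital whatever the group, and a share m has injuries for which seeing a doctor is discretionary. Amateurs see one in 40% of those cases; elites in 50%, 60% or 80%. With severe = doctor-treated or above, the rate is 0.15 + m × (share seen). The chance of a significant result in the direction of the bias is Φ[(d − 1.96 × SE₀)/SE₁], where d is the difference in rates, SE₀ the pooled and SE₁ the unpooled standard error.

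| m | Elites seen | Elite v amateur | Odds ratio | Chance of significance |
|---|---|---|---|---|
| 20% | 50% | 25% v 23% | 1.12 | 6% |
| 20% | 60% | 27% v 23% | 1.24 | 13% |
| 20% | 80% | 31% v 23% | 1.50 | 37% |
| 40% | 50% | 35% v 31% | 1.20 | 12% |
| 40% | 60% | 39% v 31% | 1.42 | 32% |
| 40% | 80% | 47% v 31% | 1.97 | 82% |
| 60% | 50% | 45% v 39% | 1.28 | 19% |
| 60% | 60% | 51% v 39% | 1.63 | 56% |
| 60% | 80% | 63% v 39% | 2.66 | 99% |

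Example (m = 40%, elites 60%): d = 0.39 − 0.31 = 0.08. The pooled rate is (39 + 93)/400 = 0.33, so SE₀ = √(0.33 × 0.67 × (1/100 + 1/300)) = 0.0543. SE₁ = √(0.39 × 0.61/100 + 0.31 × 0.69/300) = 0.0556. Then Φ[(0.08 − 0.1064)/0.0556] = Φ(−0.475) = 0.32.

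**Cut-off at emergency room or above.** Under B both groups stand at 15%, the odds ratio is 1, and access to a doctor creates no spurious difference, provided emergency room use does not itself depend on access.

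The result thus turns on two things the documents do not give: the cut-off and the access gap.

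**The case against.** A reader might infer that elites do have easier access to doctors and that the trial will report this as severity. The documents do not support that. Nothing in them shows an access gap, and they mention no team or race doctor. A reader might also take it as settled that Section 3 uses item 12. That is an inference, though a natural one, since no other item is labelled severity.

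The scale also has a defence. Section 2 names treatment requirement as what is measured, the first answer is worded as need, and level of care does partly reflect severity. The stated aim is descriptive, and the form is said to follow existing literature, which cannot be checked here. This supports keeping item 12, but not reading it as severity without qualification.

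The regressions are fitted within each group, so they contain no elite-amateur contrast for access to distort. That stands: the direct exposure is the chi-squared comparison, and the within-group concern about predictors is weaker.

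The planned t-tests on injury-related variables may already cover days to return to sport. That is possible, but Section 3 does not list them or use them to check the severe/mild classification.

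Finally, injury type and time loss are not free of the same influence. A reported fracture or concussion may depend on having been diagnosed, and return to sport may depend on treatment and competitive incentive. They are less dependent on access, not independent of it.

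**Conclusion.** The point holds as a limit on interpretation. The outcome appears to be level of care, it has no stated cut-off, and the form records nothing that could separate access from severity. A difference between elites and amateurs in severe injury could therefore be one of access or care-seeking, and within a group a predictor could reflect the same thing.

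Whether this happens, and how strongly, is unknown. Under the assumed rates it is negligible with a cut at emergency room or above, or with a small access gap (6% chance of significance at the lowest setting). With a cut at doctor-treated or above and a large gap, the spurious odds ratio is about 1.6 or more. The stronger statement, that an access difference is being reported as severity, needs evidence of a gap that the documents do not contain. The data remain usable; what needs narrowing is the claim made from them.

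**What to change.** 1. In Section 3, name item 12 as the source, state in advance which of its levels count as severe, and call the outcome injury requiring that level of medical care, in the analysis and in the conclusions.
2. On the form, add a short instruction that items 13 to 16 refer to the same most severe injury as item 12. At present they name no injury, and item 10 asks about the most recent one, so riders with several injuries may answer for different events.
3. As a sensitivity analysis, repeat the elite-amateur comparison and the within-group regressions with severity defined from days to return to sport (item 15), with a threshold set in advance, and a fracture or concussion flag (item 14). Report both sets of results side by side. A rule that both must agree in direction is not advised, because its error properties are unstated.

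Cost: SAP wording, one repeat analysis, and a small wording change in five language versions, with no new item. Items 14 and 15 rely on recall and may themselves vary with diagnosis and riding level, so the repeat analysis is a check and not a replacement. The claim from item 12 becomes narrower.

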## Mountain biking Injury Questionnaire

*Thank you for agreeing to take part in this important questionnaire about mountain biking injuries. The information we can obtain from this survey may help to improve the knowledge about injury prevalence in mountain biking. With this knowledge, it may be possible to improve safety in future and prevent injury.*

*Be assured that all answers you provide will be kept in the strictest confidentiality. This survey is anonymous. Do not write your name on the survey.*

*Please tick only the most correct answer.*

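### The planned test of mild injury occurrence cannot be made from a form that grades only each rider's worst injury

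*Combined protocol and SAP*

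**What the plan says.** Section 3 (Statistical analysis plan) states: "Chi-squared tests will be applied to determine group differences of injury prevalence and the occurrence of severe, respectively mild injury events". That sentence does not name the groups. The t-tests in the same section are "between the elite and the amateur mountain bikers", and the chi-squared tests are read here as making the same comparison. The only severity coding given is for the logistic regression: "no severe injury = 0 versus severe injury = 1". The plan does not say which of the five grades in item 12 count as mild or severe.

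The questionnaire supplies the data:

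- Item 9, "Number of injuries obtained during mountain biking", takes one number with no split by severity.
- Item 12 is the only severity item. It offers five grades, from no treatment to an overnight hospital stay, with the instruction "if more than one injury occurred, choose the most severe one".
- The introduction to the form says "Please tick only the most correct answer", so a second, milder grade cannot be entered.
- Items 13 to 17 (location, type, time to return, recovery) do not grade any further injury.

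**The concern.** The plan names mild injury occurrence as something to be tested between groups, but the form does not measure it in every rider. Someone with five mild injuries and one severe injury is recorded as severe and nothing else. What can be derived is whether the worst injury was mild, which depends on severe-injury risk as well as on mild-injury risk.

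At stake is the conclusion drawn from the mild comparison. If one group has more severe injuries, more of its mild injuries are hidden. The survey could then report a group difference in mild injuries that comes from the recording rule, or miss or reverse a real one.

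**Working it through.** **Inputs.** From the documents: one worst-injury grade per rider (item 12), one unsplit count per rider (item 9), and significance at P < 0.05 (section 3; two-sided assumed). The documents give no sample size, power or injury rates, so there is no figure of the plan's own to reproduce. Assumed: any-mild risk m of 40-80%, severe risk s of 20% in group A and 20-50% in group B, 50 to 200 riders per group, and mild and severe injury independent within a rider.

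**Step 1: who is misclassified.**

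| Item 9 | Worst grade (item 12) | Any mild injury? |
|---|---|---|
| 0 | none applies | No |
| 1 | mild or severe | Known |
| More than 1 | mild | Yes |
| More than 1 | severe | Unknown |

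Only the last row is lost.

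**Step 2: consequences that need no assumed rates.** Suppose the five grades are split in two.

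- Among injured riders, mild = not severe. The two chi-squared tests are the same test with the same p-value.
- Among all riders, recorded mild = proportion injured - proportion severe, so it cannot exceed 1 - proportion severe. It is fixed by two quantities that the plan already tests.

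**Step 3: equal true mild risk.** Under independence, recorded mild = m x (1 - s). With the same m in both groups, the false difference is m x (sB - sA).

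- Smallest: 0.40 x (0.30 - 0.20) = 0.04, recorded as 32% v 28%. Chance of a significant result: about 6% at 50 per group and 9% at 100.
- Middle: 0.60 x (0.40 - 0.20) = 0.12, recorded as 48% v 36%. About 40% at 100 per group and 68% at 200.
- Largest: 0.80 x (0.50 - 0.20) = 0.24, recorded as 64% v 40%. About 68% at 50 per group and 93% at 100. If exactly these proportions were observed, chi-squared would be 11.54 (p = 0.0007) at 100 per group and 5.77 (p = 0.016) at 50.
- Equal severe risk (20% in both): the false difference is 0 and the rejection rate is the nominal 5%.

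**Step 4: a real mild difference of 50% v 65% (+15 points).**

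| Severe risk, A v B | Recorded mild, A | Recorded mild, B | Recorded difference |
|---|---|---|---|
| 20% v 20% | 0.50 x 0.80 = 40% | 0.65 x 0.80 = 52% | +12 points |
| 20% v 40% | 0.50 x 0.80 = 40% | 0.65 x 0.60 = 39% | -1 point |
| 20% v 50% | 0.50 x 0.80 = 40% | 0.65 x 0.50 = 32.5% | -7.5 points |

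In the first row, power at 100 per group falls from 57% to 40%.

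**Step 5: what can still be bounded.** In each group the true any-mild proportion lies between R and R + U. Here R is recorded mild and U is the share of riders with a severe worst injury and more than one injury. U is observable from items 9 and 12 and is at most the severe proportion. In the middle case of step 3 the widest bounds are 48% to 68% (0.48 + 0.20) and 36% to 76% (0.36 + 0.40). The difference, B minus A, then lies between 36 - 68 = -32 and 76 - 48 = +28 points. If few riders with a severe injury had others, the bounds are much tighter.

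**The case against.** The strongest reply is that the sentence in section 3 may name two levels of one rider-level classification, not two separate outcomes. The plan's only coding is rider-level and binary, which matches item 12. On that reading the test is coherent and the fault is a loose label. This is a fair possibility, but the plan speaks of the occurrence of mild injury events, nowhere says that mild means the worst injury was mild, and sets no cut-point. On that reading too, the mild test repeats the severe test among injured riders, and the outcome still needs restating.

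A reader might also go further than the documents allow in three ways.

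- One might infer that the group with more severe injuries must show fewer mild ones. That does not follow. With assumed mild risk of 60% v 80% and severe risk of 20% v 30%, recorded mild is 0.60 x 0.80 = 48% v 0.80 x 0.70 = 56%: the right direction, though 20 points have shrunk to 8.
- One might infer that mild occurrence is wholly lost. Step 1 shows that only one class of rider is unclassifiable, and step 5 that bounds can be calculated.
- One might take the 24-point case as typical. It is the top of an assumed range; at the bottom the rejection rate is close to nominal.

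Finally, one comparison is affected in a survey whose stated aim is descriptive. That limits the weight of the point without removing it.

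**Conclusion.** The mismatch between the planned mild-injury test and the form is real, and no other item repairs it. It affects riders with a severe worst injury and more than one injury. The redundancy and the ceiling in step 2 follow from the form once its grades are split in two. The size of any distortion does not: the 4 to 24 points rest on assumed rates and independence, and a false difference arises only if severe risk differs between the groups. If severe risk is equal, a real difference is merely diluted.

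The point should not be read as a fault in the severe-injury analyses. A worst-injury grade identifies every rider with at least one severe injury, so the severe comparison and the logistic regression stand, as does overall injury prevalence. The change is worth making because it costs almost nothing and prevents a claim about mild injuries that the data cannot support.

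**What to change.** In section 3, replace the separate test of mild injury occurrence with one comparison of worst-injury grade across the groups: none (item 9 equal to 0), mild, severe. Fix before analysis which item 12 grades fall on each side of the cut. Report the result as grade of worst injury, not as occurrence of mild injuries. The cost is one or two sentences in the plan and one fewer claim.

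Option, if the form can still be changed: ask how many injuries fell in each of the five item 12 grades, and derive any mild and any severe injury from those counts. This would measure mild occurrence directly. It adds number fields in every language version and more response burden. It also adds recall error, since item 9 sets no time window and untreated injuries may be poorly remembered. It is therefore an option and not the main recommendation.
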